Figure 3.1:3 schematic overview treatment decision responders

- Patients *without combined perianal fistula remission* (irrespective of period 1 treatment) will be treated with BI 655130 1200 mg i.v. every 4 weeks (week 12, week 16 and week 20) as shown in [figure 3.1:4](#). Such patients originally assigned to placebo will thus switch to active drug.

[figure not shown]

Figure 3.1:4 schematic overview treatment decision non-responders

Follow-up period:

Patients who terminate study drug early or do not enrol into the subsequent long-term extension study 1368-0007, will continue safety follow up until 16 weeks after last study drug

administration. These patients, who drop out of the study, will receive standard of care treatment per investigator's discretion.

*Patients who complete the EOT visit* (visit 9, week 24) in period 2 of this study and who have individual clinical benefit may enter the long-term extension study 1368-0007, which offers open label active treatment with subcutaneous BI 655130.

Background therapy for underlying CD with conventional immunosuppressants or anti-TNF  $\alpha$  compounds (provided that is allowed (cf. [section 4.2.1](#))).

Individual patient participation is concluded when the patient has completed the last planned visit.

The end of the trial is defined as "last patient out", i.e. last scheduled visit completed by last patient.

An interim analysis of the Study Cohort is planned, please refer to [section 7.4](#)

An overview of all relevant trial activities is provided in the [Flow Chart](#). For visit schedules and details of trial procedures at selected visits, refer to [Section 6.1](#) and [Section 6.2](#), respectively.

Table 3.1:1 Study definitions

Rescue Medication	New or increase in dose of any medication applied to treat new or persisting symptoms related to CD
Disease worsening	Worsening of clinical status or symptoms of CD requiring administration of rescue medication in the investigator's opinion – in patients without a clinical response

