6.6 HANDLING OF MISSING DATA AND OUTLIERS

Section 7.5 of the CTP describes the handling of missing data.

Based on the different reasons for patients' data missing, different approaches will be used to assess the impact of missing data on the endpoints of this trial, depending upon the type of the endpoint. The following approaches are applied in this trial:

- The original results (OR) approach implies the presentation of data exactly as observed (not using time windows as described in [Section 6.7](#) and not setting values to missing). OR analysis will be performed on parameters and endpoints for which it is not meaningful to apply any imputation rule for the replacement of missing values.
- Observed cases (OC) approach will include all collected data, without imputation for any missing data but all values measured after any use of rescue medication will be excluded from the analysis. Note that patients that took rescue treatment are not kept in the denominator for categorical endpoints at subsequent time points.
- Observed cases including rescue (OC-IR) approach is an extension of the OC approach which includes additionally all values which were measured after rescue medication intake.
- The no response imputation (NRI) approach is applied for binary endpoints. Missing values will be imputed described in the following:
 1. If a patient takes a rescue medication (as defined in [Section 5.4.3](#)) for the treatment of disease under study or died due to any cause, then all data subsequent to the intake of such rescue will be considered to be missing.
 2. For endpoints which are measured at multiple visits, if there are data at visits both before and after the visit with a missing outcome, then impute as success only if both neighbouring visits also represent a success (independent of whether the preceding and following observations were selected for analysis based on time windows described in [Section 6.7](#)), and there is no intervening rescue treatment use. For all patients with a missing visit outcome, impute as a failure to achieve a response.

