- Imputation technique last observation carried forward (LOCF): The LOCF approach will be used as the imputation strategy to replace missing values either at intermediate visits or due to early withdrawal from the trial. The last available value, excluding baseline, will be carried forward to all subsequent visits within the on-treatment period at which a measurement is missing. Values measured after the day of first rescue medication intake (as defined in [Section 5.4.3](#)) will be set to missing and the missing values within the on-treatment period will be imputed by LOCF.

The following sections describe which imputation approach is used for the different endpoints.

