Assignment of efficacy observations to visits based on time windows will be based on the non-imputed (observed) data after setting values after rescue medication intake to missing (if applicable, i.e. for the “LOCF” and “NRI” approaches and the “OC” approach defined in [Section 6.6](#)). Visits which were not assigned a value based on time windows will thereafter

be imputed for the NRI approaches defined in [Section 6.6](#). Imputation of efficacy endpoints (binary as well as continuous) will be performed based on all available observations, irrespective of whether the observation was selected in any time window.

For derivation of the last value during the on-treatment period, the minimum value during the on-treatment period, and the maximum value during the on-treatment period, all values during the on-treatment period (including unscheduled and repeated measurements) will be considered; these will be derived for analysis of laboratory and vital signs data. For identification of potentially clinically significant abnormal laboratory values, all values (including unscheduled and repeated measurements) will be considered.

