7.5.2 Secondary endpoints

The analysis of secondary endpoints will be based on the FAS using NRI approach and will be done by “planned treatment”.

Perianal fistula response, perianal fistula remission, and combined perianal fistula remission will be derived based on reported fistula characteristic data as described in [Section 5.2.2](#) for Week 12, and Week 24;

The proportion of patients at Week 12 will be summarized descriptively presenting patient frequencies and proportions together with 95% exact unconditional confidence intervals based on the score statistic for the risk difference spesolimab minus Placebo (if feasible) (cf. [Additional Section 9.2.](#))

[figure not shown]
[Redacted]

[Redacted]

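### The no-response-imputation neighbour rule is not stopped at the Week 12 switch, so a missing Week 12 fistula response or remission on placebo can be scored a success partly from a visit on spesolimab

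*SAP*

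**What the plan says.** SAP Section 7.5.2 sets the main method for the three secondary endpoints: "The analysis of secondary endpoints will be based on the FAS using NRI approach". Table 6.3:1 adds observed cases including rescue (OC-IR) as a sensitivity analysis.

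Item 2 of the no-response imputation (NRI) rule in SAP Section 6.6 covers a visit with a missing outcome that has data before and after it. The instruction is "then impute as success only if both neighbouring visits also represent a success", provided no rescue was used in between. The neighbouring observations need not have been selected by a time window. SAP Section 6.7 repeats this for efficacy imputation in general, which "will be performed based on all available observations, irrespective of whether the observation was selected in any time window". Item 2 then closes with: "For all patients with a missing visit outcome, impute as a failure to achieve a response".

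Protocol Section 3.1 says of patients without combined perianal fistula remission at Week 12: "Such patients originally assigned to placebo will thus switch to active drug". Spesolimab patients stay on spesolimab, and placebo patients in combined remission stay on placebo.

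**The concern.** Week 12 is the last point at which the two arms are compared as randomised on fistula outcome. After Visit 6 most of the placebo arm is expected to be on active drug. An imputation rule for Week 12 should not draw on data from after that switch, yet the neighbour rule has no such limit. Only the placebo arm can be credited with a visit on a different treatment, because spesolimab patients never change.

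The SAP also works against its own safeguard. Table 6.7:1 ends the Week 12 analysis window at the date of Visit 6, which keeps later observations out of the Week 12 value. The imputation step can let them back in.

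A second consequence concerns either arm. SAP Section 3 includes Period 2 data only as far as they exist at the preliminary lock, and it attributes later changes in Period 1 results to data corrections. A late-enrolled patient with a missing Week 12 outcome has no Week 16 record at the preliminary lock and is a failure there. The same patient could become a success at the final lock with no correction made.

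**Working it through.** The plan gives no power, effect size or expected rate to reproduce; Protocol Section 7.7 bases the sample size on feasibility. The check is therefore on the text and schedule, followed by an illustration of size.

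**Can the rule reach across the switch?**

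1. The missing visit is Week 12 (Visit 6). The neighbours in the visit schedule are Week 8 (Period 1) and Week 16 (Period 2).
2. The barrier named in item 2 is rescue. Protocol Table 3.1:1 defines rescue as new or increased medication for Crohn's symptoms and does not name the planned switch. SAP Section 5.4.3, to which Section 6.6 refers, is not visible.
3. A success at Week 8 is compatible with being switched. The switch depends on combined remission (all openings closed, plus MRI). Response in SAP Section 5.2.2 needs only half the openings closed and no new fistula. A partial responder on placebo is switched by design, as is a clinical remitter with a collection above 2 cm.
4. The Week 12 analysis outcome can be missing although the patient was switched. The SAP history table says the endpoints are recalculated and not taken from investigator tick marks. The Period 2 assignment uses the on-site assessment (Protocol Section 5.1.2). No visible text gives an assignment rule for a missing Week 12 outcome.

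**Which endpoints?**

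| Week 12 endpoint | Earlier post-baseline neighbour possible? | Affected |
|---|---|---|
| Response | Week 8, if assessed | Yes |
| Remission | Week 8, if assessed | Yes |
| Combined remission | No: the flow charts place post-baseline pelvic MRI at Visits 6 and 9 only | No |

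**What is not confirmed?** The visible part of SAP Section 7.5.2 derives the outcomes "for Week 12, and Week 24" and then breaks off at redacted text. The flow-chart rows that would show fistula assessment are redacted too. Physical examination is scheduled at Weeks 8 and 16, and the log for Global Amendment 1 mentions the same endpoints analysed at further time points. Assessments at Weeks 8 and 16 are therefore likely. Week 4 fistula data are excluded from analysis by SAP Section 5.2.2, so without a usable Week 8 record the rule could hardly apply at Week 12.

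**Size.** About 20 patients randomised 1:1 gives about 10 per arm. One imputed success moves the placebo rate by 1/10, so the risk difference (spesolimab minus placebo) falls by 0.10. The intervals are 95% exact unconditional, based on the score statistic as in SAP Section 7.5.2. They were obtained by inverting two one-sided tests at 0.025, maximised over the nuisance parameter, on a 0.01 grid. All success counts are assumptions, because the documents give none.

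| Spesolimab | Placebo 1/10 (missing = failure) | Placebo 2/10 (one success imputed across the switch) |
|---|---|---|
| 3/10 | 0.20 (-0.19 to 0.56) | 0.10 (-0.30 to 0.49) |
| 4/10 | 0.30 (-0.10 to 0.65) | 0.20 (-0.22 to 0.58) |
| 5/10 | 0.40 (-0.02 to 0.74) | 0.30 (-0.14 to 0.67) |

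The interval widths run from 0.75 (0.56 + 0.19) to 0.81 (0.67 + 0.14). The shift is small against them, but it is as much as one patient in an arm of 10 can cause.

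**The case against.** The strongest reply is that the scenario almost rules itself out. A placebo patient is switched because the site examined the fistulas at Visit 6 and found no combined remission, and that examination supplies the Week 12 outcome. A late Visit 6 does not create a gap, because the window runs to its actual date. Earlier rescue sets all later values to missing, so Week 16 could not then be a success. If Visit 6 and its dose were both missed and Week 16 was assessed before dosing, the Week 16 value is not on active drug. What remains is mainly a switched patient with incomplete fistula data in the CRF and a success at the preceding visit. The endpoints are descriptive, the OC-IR analysis imputes nothing and would show the discrepancy, and the error favours placebo. All of this stands. It makes the case rare and the severity low, but it does not make the rule right.

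The closing sentence of item 2, read literally, makes every missing outcome a failure, and then the problem disappears. But the neighbour clause would then have no effect. The two sentences conflict and need to be reconciled in any case.

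A reader might infer four stronger things that the documents do not support:

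- That last observation carried forward (LOCF) causes the same error. It moves values forward only and is not listed for these endpoints in Table 6.3:1.
- That a Week 16 success alone is enough. The preceding visit must be a success too.
- That all three secondary endpoints are exposed. Combined remission is not.
- That Week 12 is the only randomised comparison in the trial. The primary gene-expression endpoint is a randomised comparison at Week 4, has no imputation and is untouched.

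**Conclusion.** The point holds in a narrow form. As written, SAP Sections 6.6 and 6.7 allow a missing Week 12 response or remission in a switched placebo patient to be scored a success using, in part, an observation made on spesolimab. They also allow the Week 12 result to change between the preliminary and final locks without a data correction, unless the two analyses are merged as Protocol Section 7.4 permits. Each affected placebo patient lowers the risk difference by 10 percentage points in arms of 10, against spesolimab.

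This assumes that fistula status is recorded at Weeks 8 and 16, that the redacted SAP text adds no limit by treatment period, and that the closing sentence of item 2 is meant for the remaining patients only. It is a low-severity correction, made with moderate confidence.

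**What to change.** In SAP Section 6.6, NRI item 2, require both neighbouring visits to lie in the same treatment period as the missing visit, in both arms. Week 12 then has no eligible following neighbour, so state outright that a missing Week 12 outcome is a failure whatever the Period 2 data show. Reword the closing sentence so that it applies to all other patients with a missing visit outcome.

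The cost is a sentence or two and a small programming change. The downside is that a true Week 12 success with a missing record counts as a failure in either arm, which is already NRI's default.

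Separately, and of lower priority: the LOCF value "will be carried forward to all subsequent visits within the on-treatment period at which a measurement is missing", and the on-treatment phase in Table 6.1:1 covers both periods. If LOCF is used for any endpoint, do not carry Period 1 values past the first infusion on or after Visit 6.

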6.6.1 Withdrawals

The reasons for withdrawal from treatment will be reported as indicated on the eCRF.

6.6.2 Efficacy endpoints

CTP Section 7.5: *No imputations for the primary endpoint [...] are planned.*

Further binary efficacy endpoints which are measured at multiple visits will be analysed using NRI imputation strategy.

[REDACTED]

[REDACTED]

[REDACTED]

[REDACTED]

[REDACTED]

[REDACTED]

[REDACTED]

6.6.3 Safety endpoints

CTP Section 7.5: *With respect to safety evaluations, it is not planned to impute missing values.*

For safety data that are displayed by time point (or visit) of measurement, the OC-IR approach as described above will be applied (cf. [Section 6.6](#)).

[figure not shown]
The only exceptions where imputation might be necessary for safety evaluation are AE dates. Missing or incomplete AE dates are imputed according to BI standards (see “Handling of missing and incomplete AE dates” (3)).

Partial start and stop dates for concomitant medications and rescue, as well as historical medication for Crohn’s Disease will be imputed to enable subsequent calculation (but not for display) by the following “worst case” approach:

- If the day of the end date is missing, then the end date is set to last day of the month (or to the patient’s last contact date, if it is earlier than the last day of the month).

- If the day and month of the end date are missing then the end date is set to 31st of December of the year (or to the patient's last contact date, if it is earlier than the 31st of December of the year).
- If the day of the start date is missing the start date is set to first day of the month (except for rescue medication, where the first dosing day of the treatment period will be used if first dosing of the treatment period happened in the same month).
- If the day and month of the start date are missing then the start date is set to 1st January of the year (except for rescue medication, where the first dosing day/month will be used if first dosing happened in the same year).

All other cases need to be assessed by the trial team on an individual basis, using the above points as guidance.

6.6.6 RNA sequencing data

The data will be presented using the OR analysis strategy.

6.6.8 Time since first diagnosis

For incomplete information on the date of first diagnosis, time since first diagnosis will be calculated as follows:

- If the year of first diagnosis is unknown, time since first diagnosis will be set to missing.
- If day and month of the first diagnosis are unknown, time since first diagnosis will be calculated as if diagnosed on the 30th June of that year.
- If only the day of the first diagnosis is unknown, time since first diagnosis will be calculated as if diagnosed on the 15th of that month.

6.7 BASELINE, TIME WINDOWS AND CALCULATED VISITS

For the Screening Cohort, the study day will be defined relative to the day of Visit 2, which is defined as Day 1. The start date of Visit 2 will be used in case the Visit 2 procedures are split over several days. For the Study Cohort, study day will be defined relative to the day of first infusion of trial treatment (Day 1).

The following descriptions refer to the analysis of the Study Cohort.

Measurements reported with date and time and taken prior to start of administration of trial treatment will be considered pre-treatment values. Measurements reported with a date only (and no time) and taken on the day of first administration of trial treatment will also be considered pre-treatment values. These pre-treatment values will be assigned to visits according to the nominal visit number as recorded on the eCRF or as provided by the laboratory.

Adverse events reported without time on the day of first drug administration in treatment period 1 are considered as on-treatment AEs in treatment period 1. AEs reported without time on the day of first drug administration in treatment period 2 are considered as on-treatment AEs in treatment period 2. In addition, treatment-emergent adverse events which are reported with a date only (and no time) and which occur on the day preceding the first administration of trial treatment in the subsequent extension trial will be considered treatment-emergent AE in this parent trial.

Baseline, unless otherwise specified, is defined as the last measurement collected prior to the start of administration of the trial treatment. For the analysis of the gene expression values (primary endpoint), baseline is the measurement at Visit 1c.

Measurements taken after start of administration of trial treatment will be considered either on- or off-treatment values based on the definition in [Section 6.1](#) and will be assigned to visits for statistical analysis, if applicable, as defined below ([Table 6.7: 1](#)).

Analysis of AE data, concomitant medication or non-drug therapies, as well as use of rescue medication will not be based on visits. Therefore, no assignment to time windows will be necessary. Frequency tables for these data will be using on-treatment data only.

Assignment of efficacy observations to visits based on time windows will be based on the non-imputed (observed) data after setting values after rescue medication intake to missing (if applicable, i.e. for the “LOCF” and “NRI” approaches and the “OC” approach defined in [Section 6.6](#)). Visits which were not assigned a value based on time windows will thereafter

be imputed for the NRI approaches defined in [Section 6.6](#). Imputation of efficacy endpoints (binary as well as continuous) will be performed based on all available observations, irrespective of whether the observation was selected in any time window.

For derivation of the last value during the on-treatment period, the minimum value during the on-treatment period, and the maximum value during the on-treatment period, all values during the on-treatment period (including unscheduled and repeated measurements) will be considered; these will be derived for analysis of laboratory and vital signs data. For identification of potentially clinically significant abnormal laboratory values, all values (including unscheduled and repeated measurements) will be considered.

7. PLANNED ANALYSIS

The format of the listings and tables will follow the BI standards “Standards for Reporting of Clinical Trials and Project Summaries” (6).

The individual values of all patients will be listed separately for the Screening Cohort and the Study Cohort. Listings will generally be sorted by country, centre number, patient number and visit (if visit is applicable in the respective listing). In the listings the visits will be labeled, i.e., for Visit 6 the label Week 12 will be presented. AE listings will be sorted by assigned treatment (see [Section 7.8.1](#) for details). The listings will be contained in Appendix 16.2 (SDL) of the CTR.

If not stated otherwise, data will be analysed as follows. Summaries of data of the Screening Cohort will be summarized overall patients. For the Study Cohort, demographics data and baseline characteristics will be summarised by treatment arm (“Placebo” and “Speso”). Summaries of data during treatment period 1 will be presented by treatment arm. Summaries over the whole treatment period will be presented by treatment sequence (“Pbo-Pbo”, “Pbo-Speso”, “Speso-Speso” and “Speso”) for visit-based data and by treatment (“Pbo (Pbo-Pbo)”, “Pbo (Pbo-Speso)”, “Speso (Pbo-Speso)”, “Speso (Speso-Speso)”, “Speso”, “Total Pbo” and “Total Speso”) for event-based data. Further details are described in [Section 6.1](#).

The following standard descriptive statistical parameters will be displayed in summary tables of continuous variables:

N	number of non-missing observations
Mean	arithmetic mean
SD	standard deviation
Min	minimum
Q1	lower quartile
Median	median
Q3	upper quartile
Max	maximum

Statistical parameters will be displayed to a defined number of decimal places as specified in the BI standards “Standards for Reporting of Clinical Trials and Project Summaries” (6).

Tabulations of frequencies for categorical data will include all possible categories and will display the number of observations in a category as well as the percentage (%) relative to the respective treatment. Percentages will be rounded to one decimal place. The category missing will be displayed if and only if there actually are missing values. Percentages will be based on all patients in the respective patient set whether they have non-missing values or not.

For the Screening Cohort, disposition of the patient population participating in the trial will be summarised by the presentation of the frequency of patients enrolled, entered, who completed the trial and who were prematurely discontinued from trial, by reason.

For the Study Cohort, disposition of the patient population participating in the trial will be summarised by the presentation of the frequency of patients enrolled, enrolled but not randomised, randomised, randomised but not treated, treated, who completed trial medication overall/ in period 1/ in period 2, who were prematurely discontinued from trial medication overall/ in period 1/ in period 2, by reason, who completed participation in the trial overall/ in period 1/ in period 2, who were prematurely discontinued from trial overall/ in period 1/ in period 2, by reason, and who entered the extension trial 1368-0007. The summary will be presented by randomised treatment. Further disposition information may be summarised by country.

In addition, number and proportion of patients assigned to spesolimab or placebo, with at least one intake of study drug in period 2 will be presented by outcome (achievement of combined perianal fistula remission after treatment period 1) and by randomised treatment.

The frequency of patients with iPDs, also summarised by whether or not the iPD led to exclusion from the any analysis set, will be presented. An iPD might lead to an exclusion from all analyses sets or from one or more analysis sets used for the efficacy analysis (i.e., RSS and FAS). The analysis will be based on the ENTS for the Screening Cohort and based on the FAS for the Study Cohort. The frequency of patients in each of the different analysis sets will also be presented. The analysis will be performed for both cohorts.

